1. BACKGROUND AND RATIONALE

Chronic macular diseases, such as age-related macular degeneration (AMD) and diabetic macular edema (DME) affect more than 28 million people worldwide and are currently the most common cause of irreversible vision loss and blindness in older adults in developed countries¹⁻⁵. Vision loss from macular diseases has been related to loss of independence in activities of daily living (ADLs) and a reduced quality of life (QoL)^{6,7}. For both neovascular AMD (nAMD) and DME, intravitreal injection treatment (IVT) of anti-vascular endothelial growth factor (anti-VEGF) is the gold standard treatment with excellent visual functional improvements in a large majority of patients⁸⁻¹². An intensive IVT regimen, especially in the first 2 years of the diagnosis, should be prioritized for optimal treatment outcomes¹³⁻¹⁵. However, real-world studies looking at long term IVT treatment in nAMD and DME have shown that visual outcomes compared to clinical trials are inferior, largely driven by a lower number of intravitreal injections administered¹⁶⁻¹⁸. Especially, non-adherence to long-term treatment and follow-up regimens in the management of patients with nAMD and DME in real-world ophthalmic care is common, with an estimated prevalence of 30-95%, and reduces the effectiveness of clinical treatment outcomes, conferring a higher risk for significant, permanent vision loss¹⁹⁻²³. Frequent and long-term IVT imposes a substantial burden on patients, and caregivers^{24,25}, with the most common reasons for non-adherence including patients' dissatisfaction with their vision, treatment-related anxiety, financial considerations, transport burden and access to appointments¹⁹. ***No studies to our knowledge have assessed the effectiveness of personalized patient-centred interventions to improve adherence to long term IVT treatment***^{19,22,26}.

Patient reported outcome measures (PROMs) can be used to measure various aspects of QoL, including emotional reactions to vision loss and treatment, financial concerns and treatment burden, similar issues that influence non-adherence to IVT¹⁹. ***Currently, PROMs are not part of standard clinical care, and there is currently a lack of standardised guidelines for clinicians to effectively manage QoL concerns and recommend appropriate interventions.*** Moreover, traditional PROMS are fixed length and burdensome to complete, hence posing significant barriers to widespread clinical implementation. Item banking and artificial intelligence (AI)-driven ***computerised adaptive testings (CATs) offer a promising and novel solution to feasibly assess QoL in a clinical setting***²⁷. A critical component of a CAT is an item bank (IB), which is a repository of items (questions) measuring a patient-reported construct (e.g., activity limitation) that have been calibrated on an interval-level scale using psychometric methods like Rasch analysis²⁷. Thereafter the CAT algorithm chooses items from the IB that are most informative at that particular point of the test and continues to offer similar items until a stopping criterion (e.g. measurement precision, based on standard error of measurement [SEM] or an item cap) is reached²⁸, to obtain a precise score with less time. Additionally, CATs can be administered in-clinic or self-administered remotely on a patient's phone, tablet or computer, offering an efficient and flexible means of estimating patients' level of QoL^{29,30}. Singapore Eye Research institute (SERI)/Singapore National Eye Centre (SNEC) have developed and validated several QoL CATs for nAMD^{31,32} and DME³³⁻³⁶ and, using our online end-to-end MoH/Synapse approved platform, customized CAT reports are available in real-time and deposited in the EMR system at SNEC.³⁷

Our novel proposed approach to improve adherence to IVT is ***personalized patient-centred care comprising a multidisciplinary protocolized intervention (MPI), which consists of medical consultation, to optimize the treatment regimen, and combinations of appropriate***

referrals to either (1) a nurse-directed patient education program (NE), (2) a low vision optometrist (OP), (3) an occupational therapy services (OT) and/or (4) a medical social worker (SW). CATs specific to AMD and DME will be used to measure QoL by collecting scores in various patient-informed domains. Lower scores at baseline, or a significant reduction in scores on follow-up visits in the various domains, will inform potential areas to address and tailor our MPI accordingly. For example, IVT patients who score poorly in the emotional domains will be sent to our IVT nurse counsellor to address patient expectations and treatment anxiety. Others, who may score poorly in the economic domains, will be referred to a medical SW to be assessed for financial aid. **There are limited studies on the effectiveness of similar multi-disciplinary allied health interventions in managing and improving adherence in IVT patients.** Previous studies testing allied health interventions did show significant improvements in QoL but have been limited to only patients with significant permanent visual impairment and were non-disease specific³⁸⁻⁴¹. **Hence, using a randomized control trial (RCT) design, we hypothesize that the MPI, a personalized intervention based on specific sub-optimal QoL domain scores, versus standard care, will lead to improved adherence rates, as well as improved clinical and QoL outcomes as measured by disease-specific CAT scores, compared to standard care and will be an appropriate, acceptable and feasible intervention, that is cost-effective for future implementation.**

If the MPI is assessed to be an effective intervention to improve adherence (Specific aim 1), QoL (Specific aim 2A) and clinical outcomes (Specific aim 2B), it would be crucial to assess implementation outcomes such as acceptability, adoptability, appropriateness, feasibility, fidelity and cost-effectiveness to plan scaling up and incorporation into clinical practice. Interviews with key stakeholders such as clinicians, nurses, allied health professionals, patients and caregivers will be essential to understand the enablers and barriers to MPI implementation (Specific aim 3). Models used to predict the MPI effect on reducing vision loss and improving QALYs, long-term will assess the cost-effectiveness of MPI (Specific aim 4).

THE MULTIDISCIPLINARY PROTOCOLISED INTERVENTION (MPI) BASED ON SUBOPTIMAL DOMAIN CAT SCORES

The proposed MPI consists of a medical consultation to optimise patients' treatment regimen, address concerns about their disease and treatment, explain advantages and disadvantages about the type of IVT medication and potential of increased treatment intervals between IVT, and address other patient and care-giver concerns.

Importantly, CAT scores will be available to the clinician to guide the consultation. Based on sub-optimal CAT scores, referral to one or a combination of services will be initiated by the study team according to a preset protocol (**Table 2**):

- (1) a referral to NE, which would include a session with a trained IVT nurse educator, who would use previously validated hard copy and digital education resources to educate the patients on their disease, symptoms, progression, and need for treatment. Factors which may cause anxiety for IVT patients such as side effects and adverse events will be addressed and the need for IVT adherence to maintain long-term vision will be reinforced. The patients would be reminded about the availability of the IVT hotline to address concerns and appointment issues.

- (2) a referral to OP who, after a needs assessment, would then carry out a comprehensive low vision assessment that includes refraction, CS, reading acuity, determination of reading goals and prescribing of suitable optical aids. OPs will assess and address any vision-related issues that may hinder reading specific tasks, navigation and other ADLs, which may be barriers to IVT adherence. They can further discuss the patient's expectations about their visual recovery and the need for IVT to maintain vision.
- (3) a referral to OT who, after a needs assessment, would provide advice about optimal lighting and, contrast perform activities of daily living retraining and functional/community mobility training, provide patient/family education and, if required, home modification to facilitate independence in ADLs, which may may allow better access to IVT appointments promoting adherence.
- (4) a referral to medical SW who, after a needs assessment, would provide the necessary emotional counselling, financial counselling and referral to community care services and other relevant support services addressing relevant barriers related to adherence to IVT.

2. HYPOTHESIS AND OBJECTIVES

Specific aim 1: To assess the effectiveness of MPI, versus standard care, in improving adherence to IVT follow-up appointments at 6, 12 and 18 months (main timepoint for primary outcome) *in patients with nAMD and DME requiring long term management* (primary outcome).

Hypothesis 1: *Compared to those in standard care, patients in the MPI group will have higher adherence to long-term follow-up appointments and IVT therapy.*

Specific aim 2A: Assess the effectiveness of MPI, versus standard care, in improving domain-specific CAT scores at the various follow-up timepoints (secondary outcome).

Hypothesis 2A: *Compared to those in standard care, patients in the MPI group will have greater gains in domain-specific CAT scores at each follow-up time point.*

Specific aim 2B: Assess the effectiveness of MPI versus standard care in improving visual acuity (VA), contrast sensitivity (CS), disease free intervals between IVT (as measured on optical coherence tomography (OCT) (secondary outcomes).

Hypothesis 2B: *Compared to those in standard care, patients in the MPI group will have greater VA and CS gains and achieve longer disease-free intervals between IVT at each follow-up time point.*

Specific Aim 3: To assess implementation outcomes of the MPI such as acceptability, adoptability, appropriateness, feasibility, fidelity.

Hypothesis 3: *Using a mixed methodology, with quantitative and qualitative outcome measures as reported by patients, caregivers, clinicians, nurses and allied health professionals, MPI will be an appropriate, adoptable, acceptable, feasible intervention with good fidelity.*

Specific Aim 4: To assess the cost-effectiveness of the MPI for improving adherence to IVT, considering its potential impact on long term visual acuity (VA) loss and QoL adjusted years (QALYs)

Hypothesis 4: *The MPI is incrementally cost-effective relative to standard care, based on accepted willingness-to-pay thresholds⁴².*

3. EXPECTED RISKS AND BENEFITS

There will be minimal risks involved as this intervention consist of counselling and supportive interventions to promote adherence. The participant is encouraged to raise any queries related to the questionnaires and the proposed interventions. The standard risks that apply to a standard consultation apply. There may also be other risks associated with the study that we are currently unable to foresee. Dilation of the pupil has risks involved such as potential angle closure glaucoma, however it will be performed as part of standard clinical care.

Benefits to the patient include the chance to participate in this fully funded study that aims to assess protocolised supportive interventions to promote adherence to intravitreal therapy based on sub-optimal PROMs. Improved adherence rates will lead to reduced rates of visual impairment, better disease control and ultimately contribute to better quality of life outcomes.

4. STUDY POPULATION

4.1. List the number and nature of subjects to be enrolled.

The study population will be recruited from retinal outpatient clinics in SNEC. There are no restrictions of recruitment based on race or sex. Assuming a maximum 20% dropout in the study we estimate a sample size of 200 patients.

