5. STUDY DESIGN AND PROCEDURES/METHODOLOGY

This study comprises two study designs running in parallel: (Cohort 1) Comprises of a prospective randomized control trial (RCT) study with two arms to assess the overall effectiveness of MPI, a personalized intervention based on the use of specific sub-optimal CAT QoL domain scores, versus standard care, to improve adherence rates to IVT, and improvements in QoL, VA, and CS, and to increase disease free intervals assessed on OCT, in patients with nAMD or DME receiving IVT and having suboptimal CAT scores. atSNEC; (Cohort 2) For those patients who do not have suboptimal CAT scores, they will continue to be enrolled in a prospective observational cohort study, and undergo routine clinical care.

- Participants who meet the eligibility criteria and provide informed consent will be enrolled and assigned a unique study identification number, before proceeding with study procedures.
- CAT scores will be collected via a hybrid remote or in-clinic delivery method. At baseline, CATs will be administered in-clinic or via CAT links sent by WhatsApp to their contact number. At subsequent timepoints, relevant CAT links will be sent via a WhatsApp message to their designated contact number, to complete the questionnaire remotely on their own SMART device, before their appointment (**Figure 1**). Those who are unable to complete CAT testing remotely will be given an additional opportunity to complete them in-clinic using an internet enabled tablet in person at their clinic visit with/without CRC assistance (**Figure 1**). The CAT scores will be assessed by clinical research coordinator.

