- Following baseline assessment, **participants with suboptimal CAT scores (Cohort 1-<50 in any domain)** will be included in the RCT and randomly allocated in a 1:1 ratio to either the intervention group (personalised multi-disciplinary protocolised intervention, MPI) or the control group (standard care). Randomisation will be conducted using a computer-generated random sequence created by an independent biostatistician not involved in recruitment or outcome assessment. To ensure balance across disease types, randomisation will be stratified by diagnosis (neovascular age-related macular degeneration [nAMD] vs. diabetic macular edema [DME]). Allocation concealment will be maintained using sequentially numbered, opaque, sealed envelopes prepared by an independent study coordinator. The envelopes will only be opened after baseline data collection to assign participants to their respective groups. Co-Is that are not treating clinicians and data analysts will remain blinded to group allocation, although masking of participants and principal investigator and Co-Is who are the treating clinicians will not be feasible due to the nature of the intervention.

- For the MPI arm, the CAT scores integrated into the electronic medical records will be used to formulate **an automated protocolized standardized MPI for all patients based on the domain specific scores that are sub-optimal** (See **Table 2**). All MPI patients will receive *a medical consultation (compulsory) and an addition of Intervention 1-4 (electives, 1) NE, 2) OP, 3) OT, 4) SW*. In the MPI arm, these referrals would be automatically triggered by the study team based on baseline CAT scores and the treating clinician will be informed. The MPI visits will take place on the same day as standard clinical visits where possible, however additional MPI study visits may be needed if there are scheduling challenges. Referral adherence to the MPI appointments and intervention will be assessed.

Sub-optimal scores are defined as any domain where the scores are below 50 at baseline or have reduced by 25% from the baseline visit. Table 2 summarizes the MPI interventions that are relevant to each CAT domain. A tailored MPI will be formulated and recommended to the patient at baseline, or at a follow-up time-points where domain scores decrease, and the MPI should be completed within 4 months.

Table 2: Standardised personalised MPI based on sub-optimal CAT domain-specific scores

| Ret CAT | | MacCAT | |

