8. SAMPLE SIZE AND STATISTICAL METHODS

8.1. Determination of Sample Size

Specific Aim 1 and 2: The primary outcome comparison of adherence rates to IVT treatment between the MPI arm versus standard care at various follow-up time points with 18 months as the main time point. It is estimated that the baseline non-adherence rate with standard care arm is 40% (SD=2). Considering a reduction of the non-adherence rate to 20% as a clinically significant difference, and assuming a power of 80% and a two-sided level of significance at 5%, the minimum sample size

required is 79 patients per arm (rounded up to 160 patients in total). Assuming a maximum 20% dropout in the study we estimate a sample size of 200 patients (Specific aim 1).

For secondary outcomes such as the improvement of QoL as assessed by the various CAT domain scores, we assume a modest effect size difference of 0.5 between the two arms. Using a power of 80%, a two-sided level of significance at 5%, and the maximum 20% dropout rate, we estimate the required sample size is 158 (79 per arm) (Specific aim 2A). Hence, this is included in the larger sample size calculated above.

Specific aim 3: There is no *a priori* sample size required for qualitative interviews. We will continue our semi-structured interviews until thematic saturation is reached (i.e. no new themes emerge). Based on previous studies by our group^{31,67}, we anticipate the need to interview between 5-10 participants for each stakeholder group to obtain data saturation, broadly: (a) clinicians using CATs and MPI, (b) NE, OP, OT and SW involved in administering MPI (c) patients involved in this study, and (d) caregivers of patients. For the purposes of estimating a budget for this grant proposal, we state an indicative sample size of 40 interview participants i.e. 10 in total for stakeholder group a and b, and 30 for stakeholder group c and d (patients and caregivers).

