14. FUNDING AND INSURANCE

Funding will be provided by the NMRC HPHSR Clinician Scientist Award (INV category) Application number MOH-HCSAINV25jan-0006.

Research participants will be provided transport allowance for their visits (SGD \$20 per patient) for all patients who enrol in the study (Cohort 1 and 2) to be collected at the exit visit of the study timed to

be similar to clinical visits. For the Cohort 1 patients, they will also be reimbursed at each study visit (\$20/visit) and compensation for their time during the qualitative interviews (SGD \$50/patient).

List of Attachments

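### The 200 patients are derived as the number to randomise but given as the number to enrol, and enrolment includes a cohort that is not randomised at baseline

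*Protocol*

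**What the plan says.** Protocol section 8.1 sizes the trial on the primary comparison of the two arms. It takes non-adherence of 40% under standard care and treats a fall to 20% as the difference to detect, "assuming a power of 80% and a two-sided level of significance at 5"%. From this it concludes that the minimum "required is 79 patients per arm (rounded up to 160 patients in total"), and it raises 160 to 200 for dropout.

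Section 4.1, whose heading asks for the number and nature of subjects to be enrolled, gives the same figure: "Assuming a maximum 20% dropout in the study we estimate a sample size of 200 patients".

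Section 5 sets out who is enrolled and who is randomised:
- Patients are enrolled once they are eligible and have consented, before any study procedure. A sub-optimal CAT score is not among the inclusion criteria in section 4.3.
- After the baseline assessment, only "participants with suboptimal CAT scores (Cohort 1-<50 in any domain") enter the RCT, allocated 1:1.
- The remainder form Cohort 2: "For those patients who do not have suboptimal CAT scores, they will continue to be enrolled in a prospective observational cohort study". They are randomised later only if their scores fall far enough. Otherwise they are followed without randomisation.

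Section 14 uses the word in the same way when it describes "all patients who enrol in the study (Cohort 1 and 2"). The protocol gives no expected split between the cohorts and no other enrolment total.

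**The concern.** The same 200 is used for two different quantities. In section 8.1 it must be the number randomised, because every step leading to it concerns the two arms. In section 4.1 it is the number enrolled, and sections 5 and 14 make enrolment wider than randomisation. The two agree only if practically every enrolled patient is eventually randomised, yet the protocol sets up a whole cohort for patients who may never be.

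At stake is when recruitment stops. A study team working from section 4.1 could close recruitment at 200 consented patients. The randomised comparison would then be smaller than the one for which 80% power is claimed on the primary outcome, and patients not recruited cannot be added at the analysis stage.

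**Working it through.** **Inputs.** All come from Protocol section 8.1 except the last.
- Standard care: "It is estimated that the baseline non-adherence rate with standard care arm is 40% (SD=2"). The SD attached to this proportion plays no part in the calculation.
- MPI arm: "Considering a reduction of the non-adherence rate to 20% as a clinically significant difference".
- Two-sided 5% level, 80% power, 1:1 allocation, dropout of at most 20%.
- Share of enrolled patients who are randomised, s: not given in the protocol, so treated as an assumption and varied.

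**Reproducing the plan's figures.** The unpooled normal formula gives, per arm,

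n = (1.960 + 0.842)² × (0.40×0.60 + 0.20×0.80) / (0.40 − 0.20)² = 7.85 × 0.40 / 0.04 = 78.5, so 79.

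Two arms make 158, rounded to 160, and 160 / (1 − 0.20) = 200. All three stated figures reproduce, so there is no arithmetic error.

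**Reserve for Cohort 2.** 200 × 0.8 = 160 evaluable, against a need of 2 × 79 = 158. If 200 is total enrolment, evaluable randomised patients number 200 × s × 0.8 = 160s. This falls below 158 once s < 158/160 = 0.9875, that is, once a little over 1% of those enrolled are never randomised. The only slack is the rounding of 158 to 160.

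**Power if 200 is total enrolment.** Dropout is held at 20%. Power is for the Pearson chi-square test, 40% against 20%, by exact enumeration of the two binomial distributions. The last column is the total enrolment needed to randomise 200, which is 200/s rounded up.

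| Assumed s | Randomised (200s) | Evaluable per arm (80s) | Exact power | Enrolment needed to randomise 200 |
|---|---|---|---|---|
| 100% | 200 | 80 | 80.1% | 200 |
| 90% | 180 | 72 | 75.7% | 223 |
| 80% | 160 | 64 | 70.7% | 250 |
| 60% | 120 | 48 | 58.6% | 334 |
| 50% | 100 | 40 | 49.7% | 400 |

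Fisher's exact test, the alternative named in section 8.2, is left out of the table. It gives 74.5% even with all 200 randomised (80 evaluable per arm). That deficit comes from the choice of test, has nothing to do with Cohort 2, and is a separate matter.

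**The case against.** The strongest reply is that 200 plainly means the randomised patients. Section 8.1 ties the figure to Specific aim 1, and section 5 confines that comparison to Cohort 1. Section 4.1 only repeats the sentence from 8.1; the word enrolled stands in its heading, which reads like a form prompt, and the section sets no cap or stopping rule. This is a fair reading, and under it the power is intact. It does not remove the inconsistency: section 4.1 then reports the wrong quantity as enrolment, and the real total appears nowhere.

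Three further points limit the size of the problem.
- **Dropout.** 20% is called a maximum. At s = 90% and 10% dropout, 180 × 0.9 = 162 patients remain, or 81 per arm, which exceeds 79. Lower dropout could therefore absorb a modest Cohort 2. But 200 was built on 20%, and the protocol does not plan on less.
- **The randomised share.** Entry to the RCT needs a score below 50 in any one of several domains (Table 2 lists eight for RetCAT and five for MacCAT). The share could be high, and nothing in the protocol shows that the 50% or 60% rows are likely.
- **Late randomisation.** Cohort 2 patients whose scores fall join the RCT and add to its numbers. A reader might infer that they cannot help because they lack 18 months of follow-up. The documents do not settle this. Section 5 does not say when the outcome clock starts for them, and section 7.1 collects records up to 24 months after consent, so a patient randomised at month 6 could have about 18 months of record data. Later entrants would have less. The protocol neither quantifies this route nor says how their 18-month outcome is timed.

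**Conclusion.** The protocol is internally inconsistent about what its 200 patients are, and the inconsistency bears on the stated power for the primary outcome. That holds on either reading. If 200 is total enrolment, there is no room for Cohort 2 at the planned dropout, and power falls below the stated 80%, for example to about 76% if 90% are randomised and 71% if 80% are. If 200 is the number randomised, power stands and section 4.1 understates enrolment by however many patients are never randomised.

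A reader might go further and conclude that the RCT will be underpowered. The documents do not support that as a fact: it needs both the total-enrolment reading and a never-randomised share that neither lower dropout nor late randomisation makes good. The power figures rest on the plan's own 40% and 20% rates, dropout at its stated ceiling, no late entrants beyond the assumed share s, and values of s that are assumptions.

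**What to change.** In sections 4.1 and 8.1, state that 200 is the number randomised in Cohort 1 (100 per arm) and that recruitment continues until it is reached. Give total enrolment, Cohorts 1 and 2 together, as a separate figure equal to 200 divided by an assumed Cohort 1 share, with the basis for that share. If patients randomised later from Cohort 2 are to count towards the 200, say so, and state from when their 18-month outcome is measured.

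If total enrolment is in fact capped at 200, restate the expected number randomised and the lower power that goes with it.

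The wording costs a couple of sentences in a protocol amendment. The practical cost is either more patients to consent and follow (50 more at a share of 80%, since 250 − 200 = 50) or a less favourable power statement. It should be settled before recruitment closes.
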